9.3.1.2.3 Schedule for PK sample collection for Part 1 (Phase 1b) Schedule C

Cycle (C), day (D)	Timing of PK sample blood draws	PK for
C1, D7	Pre-dose navitoclax (0h), 2h (+/-5 min,)	Navitoclax and
	4h (+/-5min,) 6h (+/-5 min,) 8h (+/-24	trametinib
	min)	
C1, D8	Pre-dose navitoclax (0h), (will represent	Navitoclax and
	24h post-dose from prior day)	trametinib
C1, D14 [#]	Pre-dose navitoclax (0h), 2h (+/- 5	Navitoclax and
	min,) 4h (+/-5 min,) 6h (+/- 5 min,) 8h	trametinib
	(+/- 24 min)	
C1, D15#	Pre-dose navitoclax (0h)	Navitoclax and
	(will represent 23h post-dose navitoclax	trametinib
	from prior day, +/- 1 hr)	
C2, D1	Pre-dose navitoclax (single trough	Navitoclax and
	level)	trametinib
C4, D1	Pre-dose navitoclax (single trough	Navitoclax and
	level)	trametinib
C8, D1	Pre-dose navitoclax (single trough	Navitoclax and
	level)	trametinib
C12, D1	Pre-dose navitoclax (single trough	Navitoclax and
	level)	trametinib

Version Date: July 22, 2022

9.3.1.2.4 Schedule for PK sample collection for Part 2 (Phase 2)

Cycle (C), day (D)	Timing of PK sample blood draws	PK for
C2, D1	Pre-dose trametinib	Navitoclax and trametinib
C4, D1	Pre-dose trametinib	Navitoclax and trametinib
C8, D1	Pre-dose trametinib	Navitoclax and trametinib
C12, D1	Pre-dose trametinib	Navitoclax and trametinib

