
Table 5.2: Schedule of Agent Administration

Schedule A and B:

	Reg	gimen Desc	ription		
Agent	Premedications; Precautions	Dose	Route	Schedule	Cycle Length
Trametinib	Take on empty stomach, >1 hour before meal or >2 hours after meal	** tablet(s)	PO daily, >1 hour before meal or >2 hours after meal	Days 1-28	28 days (4 weeks)
Navitoclax*	Take with food.	** tablet(s)	PO in the a.m.	Days 1-28	

^{*} For days on which subjects will undergo an on-treatment biopsy, Navitoclax should be taken in the a.m. with Jello at least two hours before the scheduled biopsy.

Schedule C:

	Reg	gimen Desc	ription		
Agent	Premedications; Precautions	Dose	Route	Schedule	Cycle Length
Trametinib	Take on empty stomach, >1 hour before meal or >2 hours after meal	** tablet(s)	PO daily in the p.m., >1 hour before meal or >2 hours after meal	Days 1-14	28 days (4 weeks)
Navitoclax*	Take with food.	** tablet(s)	PO in the a.m.	Days 1-28	

^{*} For days on which subjects will undergo an on-treatment biopsy, Navitoclax should be taken in the a.m. with Jello at least two hours before the scheduled biopsy.

Table 5.3: Dose Escalation Criteria for Part 1 (Phase 1b)

Number of Patients with DLT at a Given Dose Level	Escalation Decision Rule
--	---------------------------------

^{**}Doses as appropriate for assigned dose level.

^{**}Doses as appropriate for assigned dose level.

0 out of 3	Enter 3 patients at the next dose level.
≥2	Dose escalation will be stopped. This dose level will be declared the maximally administered dose (highest dose administered). Three (3) additional patients will be entered at the next lowest dose level if only 3 patients were treated previously at that dose.
1 out of 3	 Enter at least 3 more patients at this dose level. If 0 of these 3 patients experience DLT, proceed to the next dose level. If 1 or more of this group suffer DLT, then dose escalation is stopped, and this dose is declared the maximally administered dose. Three (3) additional patients will be entered at the next lowest dose level if only 3 patients were treated previously at that dose.
≤1 out of 6 at highest dose level below the maximally administered dose	This is generally the recommended phase 2 dose. At least 6 patients must be entered at the recommended phase 2 dose.

Patients will be replaced if they are not evaluable for the DLT window.

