10. STUDY CALENDAR

Baseline evaluations are to be conducted within 2 weeks prior to start of protocol therapy. Scans and x-rays, Echocardiogram or MUGA, and ophthalmic examination must be done ≤ 4 weeks prior to the start of therapy. In the event that the patient's condition is deteriorating, laboratory evaluations should be repeated within 48 hours prior to initiation of the next cycle of therapy. All study visits have a ± -3 day window after Cycle 2, Day 1.

Labs obtained on C1, D1 must re-meet eligibility criteria.

[#] Represents 14th day of trametinib dosing under Schedule C Trametinib dosing is always in the evenings. Timing is not adjusted on PK days

Part 1 (Phase 1b) Schedule A

	Pre- Study	C1D1	C1D7	C1D8	C1D15	C1D21	C1D22	C2D1	C2D15	C3D1, C4D1, etc	Off Study ^q
Trametinib				T	T	T	T	T	T	Т	
Navitoclax		L	L	N	N	N	N	N	N	N	
Informed consent a	X										
Demographics	X										
Medical history	X										
Concurrent meds	X	X								X	
Physical exam b	X	X		X	X		X	X	X	X	X
Vital signs c	X	X	X	X	X	X	X	X	X	X	X
Height	X										
Weight	X	X		X	X		X	X	X	X	X
Performance status	X	X		X	X		X	X	X	X	X
CBC w/diff, plts	X	X	X		X		X	X	X	X	X
Serum chemistry ^d	X	X	X		X		X	X	X	X	X
PT/PTT	X	X	X				X			X	X
Tumor Markers ^e	X							X		X	X
Urinalysis	X										
EKG ^f	X	X		X	X		X	X	X		
Echocardiogram or MUGA	X	Repeat	on C1D28				l.) Thereaft ine and foll			reeks (use	
Ophthalmology exam	X		Rej	peated as	needed onl	y if patient	experience	s vision cl	hanges		
Adverse event evaluation		X								X	X
Radiologic evaluation/Tumor measurements	X	Cycle 1	Radiologic measurements (by CT or MRI) should be performed every 8 weeks following Cycle 1 Day 1. Tumor measurements are repeated every 8 weeks. Documentation (radiologic) must be provided for patients removed from study for progressive disease. h								
B-HCG i	X										

92

Version Date: July 22, 2022

Tumor biopsy	X j				Xk			
PK blood draw ^l		Xm	Xm	X ⁿ	Xn	Xº	X^{l}	
Archival Tissue	Xp							

- T: Trametinib. Dose as assigned; dose first in morning on empty stomach, at least 1 hour before food (there are no hematologic paramaters that must be met to continue dosing with trametinib at the beginning of each cycle.)
- N: Navitoclax. Dose as assigned; dose second in morning with food, at least 1 hour after trametinib
- L: Lead-in dose of navitoclax. 150 mg daily in morning for 7 days, dosed as above.
- a: Informed consent can be signed within 28 days of C1D1.

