- p: Off study procedures should be performed within 14 days of last dose. Patients will be followed until the resolution or stabilization of all study-related toxicity and for a minimum of 30 days after removal from study or until death, whichever occurs first. Patients removed from study for unacceptable adverse event(s) will be followed until resolution or stabilization of the adverse event.

Part 2 (Phase 2) Schedule C (To be used if RP2D is to be given by Schedule C)

	Pre- Study	C1D1	C1D8	C1D15	C1D22	C2D1	C2D15	C3D1, C4D1, etc	Off Study ^p
Trametinib		Т	Т			Т		Т	
Navitoclax		L	N	N	N	N	N	N	
Informed consent a	X								
Demographics	X								
Medical history	X								
Concurrent meds	X	X						X	
Physical exam ^b	X	X	X	X	X	X	X	X	X
Vital signs ^c	X	X	X	X	X	X	X	X	X
Height	X								
Weight	X	X	X	X	X	X	X	X	X
Performance status	X	X	X	X	X	X	X	X	X
CBC w/diff, plts	X	X	X	X	X	X	X	X	X
Serum chemistry ^d	X	X	X	X	X	X	X	X	X
PT/PTT	X	X	X	X		X		X	X
Tumor Markers ^e	X					X		X	
Urinalysis	X								
EKG ^f	X	X	X	X	X	X	X		
Echocardiogram or MUGA	X	Repe						after, repeat every 12 ollow up). g	

102

Ophthalmology exam	X	I	Repeated as needed only if patient experiences vision changes									
Adverse event evaluation		X	XX									
Radiologic Evaluations/Tumor measurements	X	following C Documentat	adiologic measurements (by CT or MRI) should be performed every 8 weeks llowing Cycle 1 Day 1. Tumor measurements are repeated every 8 weeks. ocumentation (radiologic) must be provided for patients removed from study for ogressive disease. h									
B-HCG	Xi											
Tumor biopsy	$X^{j,k}$		$X^{j,l}$									
PK blood draw ^m					Xn		X ^m					
Archival Tissue	Xº											
cfDNA blood draw		X			X		X					

- T: Trametinib. Dose as assigned; dose in evening on empty stomach, at least 1 hour before or two hours after food (there are no hematologic paramaters that must be met to continue dosing with trametinib at the beginning of each cycle.)
- N: Navitoclax. Dose as assigned; dose in morning with food
- L: Lead-in dose of navitoclax. 150 mg daily in morning for 7 days, dosed as above.
- a: Informed consent can be signed within 28 days of C1D1.

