- m: Complete PK schedule detailed in Section 9.3. Additional PK samples (single trough measurement only) required on day 1 of cycles 4, 8, and 12, not represented on this calendar
- n: Single pre-dose (pre-navitoclax) trough on C2D1. See Section 9.3 for details.
- o: At least 20 unstained slides are required. If a patient is having a tumor biopsy, less than 20 is acceptable with PI approval.

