Schedule for Part 1 (Phase 1b) Schedule C (All times relative to navitoclax dose, per Section 9.3)

Day of Collection	Planned Collection Time (hr)
C1D7	Pre-navitoclax (0h), 2h, 4h, 6h, 8h (for both navitoclax and trametinib)
C1D8	Pre-navitoclax (for both navitoclax and trametinib)
C1D14	Pre-navitoclax (0h), 2h, 4h, 6h, 8h (for both navitoclax and trametinib)
C1D15	Pre-navitoclax (for both navitoclax and trametinib)
C2D1	Pre-navitoclax (for both navitoclax and trametinib)
C4D1	Pre-navitoclax (for both navitoclax and trametinib)
C8D1	Pre-navitoclax (for both navitoclax and trametinib)
C12D1	Pre-navitoclax (for both navitoclax and trametinib)

Schedule for Part 2 (Phase 2)

Day of Collection	Planned Collection Time (hr)
C2D1	Pre-navitoclax (for both navitoclax and trametinib)
C4D1	Pre-navitoclax (for both navitoclax and trametinib)
C8D1	Pre-navitoclax (for both navitoclax and trametinib)
C12D1	Pre-navitoclax (for both navitoclax and trametinib)

Specimen Processing Procedures

Immediately after collection, gently invert (do not shake) the evacuated blood collection tube 8-10 times to mix the K₂EDTA anticoagulant with the whole blood. Blood samples *MUST* be placed on wet ice immediately after mixing the blood with the anticoagulant. Blood samples should be processed into plasma within 15 minutes of collection (30 minutes maximum). Centrifuge samples at 2500 to 3000 rpm for 10 to 15 minutes at 4°C to achieve a clear plasma layer over the red cells. The speed and time may be varied according to the make and model of centrifuge used. Immediately transfer plasma into two 1.0 mL Matrix TrackMate ScrewTop tubes (each containing approximately 0.75 mL of plasma) and store at -20°C until shipped. Ship all frozen plasma samples on dry ice, overnight.

Specimen Shipping Instructions

Ship PK samples to:

Covance Laboratories Inc. [name] [contact] [contact]

2) NAVITOCLAX (ABT-263) PK

PK studies will be done to assess the biodistribution of navitoclax.

Plasma concentrations of navitoclax will be measured under the direction of AbbVie. Analysis will be performed by AbbVie and the results made available to the investigators.

Navitoclax (ABT-263) PK Samples

The processing of PK samples should be performed as described below:

- 1. Collect 3 mL blood in a K2EDTA collection tube.
- 2. Immediately invert tube 8-10 times and place in ice bath or cryoblock until ready to centrifuge.

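### Part 2 PK samples are timed by trametinib in Section 9.3.1.2.4 but by navitoclax in Appendix C; under Schedule C a sample labelled as a navitoclax trough could be drawn mid-interval

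*Combined protocol and SAP*

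**What the plan says.** Section 9.3.1.2.4 has one table for Part 2, not divided by schedule. Day 1 of cycles 2, 4, 8 and 12 each carry one sample for both drugs, timed "Pre-dose trametinib". The Part 2 table in Appendix C covers the same four days and gives "Pre-navitoclax (for both navitoclax and trametinib" as the time.

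The Section 10 calendars do distinguish the schedules. Note n for Part 2 Schedules A and B puts the cycle 2 day 1 trough before both drugs. For Schedule C it reads "Single pre-dose (pre-navitoclax) trough on C2D1". Note m in all three Part 2 calendars says that the complete PK schedule is in Section 9.3, and note n for Schedules B and C also sends the reader there.

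The order of dosing differs by schedule. On PK days, Section 9.3.1.2 has trametinib taken in the morning, one hour before navitoclax. Under Schedule C, Table 5.2 gives trametinib "PO daily in the p.m., >1 hour before meal or >2 hours after meal" on days 1-14 and navitoclax in the morning on days 1-28. The Part 2 Schedule C calendar agrees ("dose in evening on empty stomach, at least 1 hour before or two hours after food"). The footnote to the Schedule C PK table in 9.3.1.2.3 adds: "Trametinib dosing is always in the evenings. Timing is not adjusted on PK days".

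**The concern.** Under Schedules A and B the two drugs are an hour apart, so timing a sample by one or the other makes little difference to navitoclax. Under Schedule C they are taken at opposite ends of the day. A draw tied to the evening trametinib dose falls in the middle of the navitoclax dosing interval, not long after its 6-9 h peak (Section 2.2.2, Clinical Pharmacokinetics).

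Schedule C is a realistic case for Part 2. Section 5.1.1 ends escalation on Schedules A and B from Protocol Version 10, and Section 10 contains a dedicated Part 2 Schedule C calendar.

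At stake is the Part 2 exposure record. Sections 9.3.1.1 and 9.3.1.5 say that the PK samples will be assessed for the endpoints in 2.5.1 and 13.4.1.1, which include the pre-dose (trough) concentration. If sites follow different tables, true navitoclax troughs and mid-interval levels could be pooled under one label.

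**Working it through.** **1. The texts side by side (Part 2, day 1 of cycles 2, 4, 8, 12)**

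| Source | Schedules A/B | Schedule C |
|---|---|---|
| Section 9.3.1.2.4 | before trametinib | before trametinib |
| Appendix C, Part 2 table | before navitoclax | before navitoclax |
| Section 10, note n (cycle 2) | before both drugs | before navitoclax |

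The Part 1 Schedule C tables (9.3.1.2.3 and Appendix C) also specify before navitoclax. For Schedule C, Section 9.3.1.2.4 is the outlier. For A/B, Appendix C differs from the other two.

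**2. Inputs for the size of the effect (Section 2.2.2)**

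- Navitoclax half-life: about 15 h (solid tumor trial M06-822) and about 17 h (lymphoid trial M06-814), both single-agent.
- Peak at about 7 h and 9 h in those trials; peak-to-trough ratio close to twofold at steady state (M06-822).
- Time from morning navitoclax to evening trametinib: not stated. **Assumed 10 to 14 h.**

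**3. Formula**

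With mono-exponential decline after the peak, the level t hours after the dose relative to the 24 h trough is

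C(t)/C(24) = 2^((24 − t)/half-life).

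Plausibility check against the documents' ratio: half-life 15 h with peak at 7 h gives 2^(17/15) = 2.19; half-life 17 h with peak at 9 h gives 2^(15/17) = 1.84. Both fit a ratio close to two.

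**4. Navitoclax under Schedule C, draw just before evening trametinib**

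| Hours after navitoclax | Half-life 15 h | Half-life 17 h |
|---|---|---|
| 10 | 2^(14/15) = 1.91 | 2^(14/17) = 1.77 |
| 12 | 2^(12/15) = 1.74 | 2^(12/17) = 1.63 |
| 14 | 2^(10/15) = 1.59 | 2^(10/17) = 1.50 |

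The sample would exceed the trough by about 50 to 90%.

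**5. Schedules A/B**

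A draw just before trametinib is 23 h after navitoclax instead of 24 h: 2^(1/15) = 1.047 and 2^(1/17) = 1.042, so 4 to 5%. For trametinib, the Appendix C wording is the weaker one: a draw immediately before navitoclax falls about 1 h after trametinib, close to its 1.5 h median time to peak after a single dose (Section 2.2.1.2).

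**6. Trametinib under Schedule C**

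Trametinib is off on days 15-28. From the evening of day 14 to day 1 of the next cycle is 14.5 days (morning draw) to 15 days (evening draw). With the 4.5-day effective half-life, the level relative to the 24 h on-treatment trough is 2^(−13.5/4.5) = 0.125 to 2^(−14/4.5) = 0.116, about 12%. Neither wording yields a trametinib dosing-interval trough on that day.

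**The case against.** The strongest reply is that one morning sample can satisfy every text. Under Schedule C a draw before morning navitoclax is also before that evening's trametinib. Section 9.3.1.2.4 carries neither the −1 h label nor the within-5-minutes footnote of the Part 1 A/B tables, and it does not use the word trough. Section 9.3.1.2 says that all draw times are relative to navitoclax, and the Schedule C calendar states the intended timing. Appendix C introduces its time points as an example.

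Much of this stands. A reader might infer that Part 2 navitoclax troughs will be overstated; the documents support only that they could be, at a site that ties the draw to the trametinib dose. That reading remains natural, because the Part 1 A/B tables define pre-dose as within 5 minutes of dosing and the calendar refers sites to the table at fault.

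Two other inferences go too far. One is that Part 2 will use Schedule C. Ending A/B escalation does not fix the schedule of the recommended dose, the Schedule C calendar is conditional ("Part 2 (Phase 2) Schedule C (To be used if RP2D is to be given by Schedule C"), and Section 5.1.2 still describes Part 2 as Schedule A or B. The other is that the Part 2 conclusions are at risk. PK is not among the Part 2 objectives or endpoints in 13.1.2.1 to 13.1.2.4, the PK analysis in 13.4.1.1 is listed for Part 1, and the two-stage response design is untouched.

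Dose times may also be partly captured already. Appendix C requires the date and time of each sample, and patients keep a dose diary. The diary form is not reproduced, so no gap in dose times can be shown.

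**Conclusion.** The sampling times for Part 2 contradict each other, and no single wording gives a trough for both drugs under every schedule. The consequence is material for navitoclax only if the recommended dose is given by Schedule C and a site draws immediately before trametinib. In that case the value would be about 1.5 to 1.9 times the 24 h trough, close to the whole peak-to-trough range. That range rests on the assumed 10 to 14 h gap, single-agent half-lives of 15 to 17 h, and simple exponential decline. A narrower figure would need a clock time that the documents do not give.

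Under A/B the effect on navitoclax is 4 to 5%, though Appendix C's timing could place the trametinib sample near its peak. No Part 2 response or safety endpoint changes. The harm is confined to the Part 2 exposure data. It is still worth correcting, because the text governs when blood is drawn and a mistimed sample cannot be redrawn.

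**What to change.** - State the sampling time by schedule in both Section 9.3.1.2.4 and the Part 2 table of Appendix C, as the calendar already does: before both drugs for Schedules A and B; before navitoclax, in the morning, for Schedule C.
- Reconcile the general PK-day dosing order in Section 9.3.1.2, which has trametinib in the morning and names only Schedules A and B, with the Schedule C footnote in 9.3.1.2.3.
- Record the time of the last dose of each drug alongside each sample, so that any off-schedule draw can be identified.
- Note that trametinib samples on day 1 of cycles 2, 4, 8 and 12 under Schedule C follow about 14 days off drug and are not dosing-interval troughs.

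The cost is a few lines in two tables, one clarifying sentence, and two dose-time fields if they are not already collected. Sample size, visits and number of blood draws do not change.

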9.3.1.3 Handling of Specimens

Procedures for specimen handling and processing are defined in APPENDIX C.

9.3.1.4 Shipping of Specimens

Procedures for specimen shipping are defined in APPENDIX C.

9.3.1.5 Sites Performing Correlative Study

Analysis of PK samples will be performed by AbbVie (for navitoclax) and GSK (for trametinib) according to established procedures, and assessed for the endpoints described in Sections 2.5.1 and 13.4.1.1. Results will be reported to investigators, and data analysis will be performed at DF/HCC in cooperation with AbbVie and GSK.

9.4 Special Studies

N/A

10. STUDY CALENDAR

Baseline evaluations are to be conducted within 2 weeks prior to start of protocol therapy. Scans and x-rays, Echocardiogram or MUGA, and ophthalmic examination must be done ≤ 4 weeks prior to the start of therapy. In the event that the patient's condition is deteriorating, laboratory evaluations should be repeated within 48 hours prior to initiation of the next cycle of therapy. All study visits have a ± -3 day window after Cycle 2, Day 1.

Labs obtained on C1, D1 must re-meet eligibility criteria.

[#] Represents 14th day of trametinib dosing under Schedule C Trametinib dosing is always in the evenings. Timing is not adjusted on PK days

Part 1 (Phase 1b) Schedule A

	Pre- Study	C1D1	C1D7	C1D8	C1D15	C1D21	C1D22	C2D1	C2D15	C3D1, C4D1, etc	Off Study ^q
Trametinib				T	T	T	T	T	T	Т	
Navitoclax		L	L	N	N	N	N	N	N	N	
Informed consent a	X										
Demographics	X										
Medical history	X										
Concurrent meds	X	X								X	
Physical exam b	X	X		X	X		X	X	X	X	X
Vital signs c	X	X	X	X	X	X	X	X	X	X	X
Height	X										
Weight	X	X		X	X		X	X	X	X	X
Performance status	X	X		X	X		X	X	X	X	X
CBC w/diff, plts	X	X	X		X		X	X	X	X	X
Serum chemistry ^d	X	X	X		X		X	X	X	X	X
PT/PTT	X	X	X				X			X	X
Tumor Markers ^e	X							X		X	X
Urinalysis	X										
EKG ^f	X	X		X	X		X	X	X		
Echocardiogram or MUGA	X	Repeat	on C1D28				l.) Thereaft ine and foll			reeks (use	
Ophthalmology exam	X		Rej	peated as	needed onl	y if patient	experience	s vision cl	hanges		
Adverse event evaluation		X								X	X
Radiologic evaluation/Tumor measurements	X	Cycle 1	Radiologic measurements (by CT or MRI) should be performed every 8 weeks following Cycle 1 Day 1. Tumor measurements are repeated every 8 weeks. Documentation (radiologic) must be provided for patients removed from study for progressive disease. h								
B-HCG i	X										

92

Version Date: July 22, 2022

Tumor biopsy	X j				Xk			
PK blood draw ^l		Xm	Xm	X ⁿ	Xn	Xº	X^{l}	
Archival Tissue	Xp							

- T: Trametinib. Dose as assigned; dose first in morning on empty stomach, at least 1 hour before food (there are no hematologic paramaters that must be met to continue dosing with trametinib at the beginning of each cycle.)
- N: Navitoclax. Dose as assigned; dose second in morning with food, at least 1 hour after trametinib
- L: Lead-in dose of navitoclax. 150 mg daily in morning for 7 days, dosed as above.
- a: Informed consent can be signed within 28 days of C1D1.
- b: Complete physical exam required pre-study and on Day 1 of each cycle, including head, eye, ear, nose, throat (HEENT,) cardiovascular, dermatological, musculoskeletal, respiratory, gastrointestinal, and neurological systems. Limited or symptom directed physical exam at the discretion of the investigator is sufficient at all other visits.
- c: Vitals should include blood pressure, heart rate, respiratory rate, oxygen saturation, and temperature.
- d: Albumin, alkaline phosphatase, total bilirubin, bicarbonate, BUN, calcium, chloride, creatinine, glucose, LDH, phosphorus, potassium, total protein, SGOT [AST], SGPT [ALT], sodium.
- e: Disease-specific tumor markers as appropriate (e.g. CEA, CA-19-9, CA125) should be drawn at specified times provided the patient has elevation of that specific tumor maker prior to study enrollment. Colorectal: CEA; Pancreatic: CEA and CA-19-9; Lung: CEA; Any other tumor types: PI with treating MD can advise which tumor markers are appropriate to follow.
- f: EKGs should be done pre-dose at all required time points.
- g: ECHO or MUGA to be performed at screening and again on C1D28 (acceptable window C1D23-D29.) Thereafter, exam should be repeated every 12 weeks (+/-1 week.) The same modality used during screening should be used for all follow up exams.
- h: Tumor measurements and radiologic evaluation should occur every 8 weeks +/- 1 week. If a patient is on a dose hold, scans should be kept on original schedule and should not be shifted. Patients that have scans which reveal disease progression do not need to repeat end of treatment scans
- i: Serum pregnancy test (women of childbearing potential) must be done within 7 days of C1D1.
- j: Pre-study tumor biopsy to occur between days -21 and day-1. When possible, it is preferred, but not required, that the pre-treatment biopsy be performed between days -7 and -1 of treatment in order to most accurately represent the baseline signaling activity prior to treatment. Platelet count and PT/PTT must be checked prior to procedure according to institutional guidelines, and must be in acceptable range as defined in section 9.1.1.2.
- k: On treatment biopsy to occur ~2 weeks after trametinib dosing on C1D22 (+/- 7 days.) Platelet count and PT/PTT must be checked prior to procedure on the same day, and must be in acceptable range as defined in section 9.1.1.2.
- 1: Complete PK schedule detailed in Section 9.3. Additional PK samples (single trough measurements only) required on day 1 of cycles 4, 8, and 12, not represented on this calendar.
- m: Includes pre-dose (0h), 2h, 4h, 6h, 8h draws on C1D7 and 23h draw (pre-dose) on C1D8. See section 9.3 for details.
- n: Includes pre- trametinib (-1h), pre navitoclax (0h), and 2h, 4h, 6h, 8h post navitoclax draws on C1D21 and 23h draw (pre- trametinib) on C1D22. See section 9.3 for details.
- o: Single pre-dose (pre- trametinib and navitoclax) trough on C2D1. See Section 9.3 for details.
- p: At least 20 unstained slides are required. If a patient is having a tumor biopsy, less than 20 is acceptable with PI approval.
- q: Off study procedures should be performed within 14 days of last dose. Patients will be followed until the resolution or stabilization of all study-related toxicity and for a minimum of 30 days after removal from study or until death, whichever occurs first. Patients removed from study for unacceptable adverse event(s) will be followed until resolution or stabilization of the adverse event.

Part 1 (Phase 1b) Schedule B

	Pre- Study	C1D1	C1D7	C1D8	C1D14	C1D15	C1D22	C2D1	C2D15	C3D1, C4D1, etc	Off Study ^q
Trametinib		T	T	Т	Т	Т	Т	T	Т	Т	
Navitoclax		L	L	N	N	N	N	N	N	N	
Informed consent a	X										
Demographics	X										
Medical history	X										
Concurrent meds	X	X-								X	
Physical exam ^b	X	X		X		X	X	X	X	X	X
Vital signs ^c	X	X	X	X	X	X	X	X	X	X	X
Height	X										
Weight	X	X		X		X	X	X	X	X	X
Performance status	X	X		X		X	X	X	X	X	X
CBC w/diff, plts	X	X	X			X	X	X	X	X	X
Serum chemistry d	X	X	X			X	X	X	X	X	X
PT/PTT	X	X	X			X		X		X	X
Tumor Markers ^e	X							X		X	X
Urinalysis	X										
EKG ^f	X	X		X		X	X	X	X		
Echocardiogram or MUGA	X	Repeat	t on C1D2		days prior o				every 12 we	eks (use	
Ophthalmology exam	X		Re	epeated as	needed only	if patient e	xperiences	vision ch	anges		
Adverse event evaluation		X-								X	X
Radiologic evaluations/ Tumor measurements	X	Cycle 1	XX Radiologic measurements (by CT or MRI) should be performed every 8 weeks following Cycle 1 Day 1. Tumor measurements are repeated every 8 weeks. Documentation (radiologic) must be provided for patients removed from study for progressive disease. h								

94

Version Date: July 22, 2022

B-HCG	Xi							
Tumor biopsy	Xj				X^k			
PK blood draw ^l		Xm	Xm	Xn	Xn	Xº	X^1	
Archival Tissue	Xp							

- T: Trametinib. Dose as assigned; dose first in morning on empty stomach, at least 1 hour before food (there are no hematologic paramaters that must be met to continue dosing with trametinib at the beginning of each cycle.)
- N: Navitoclax. Dose as assigned; dose second in morning with food, at least 1 hour after trametinib
- L: Lead-in dose of navitoclax. 150 mg daily in morning for 7 days, dosed as above.
- a: Informed consent can be signed within 28 days of C1D1.
- b: Complete physical exam required pre-study and on Day 1 of each cycle, including head, eye, ear, nose, throat (HEENT,) cardiovascular, dermatological, musculoskeletal, respiratory, gastrointestinal, and neurological systems. Limited or symptom directed physical exam at the discretion of the investigator is sufficient at all other visits.
- c: Vitals should include blood pressure, heart rate, respiratory rate, oxygen saturation, and temperature.
- d: Albumin, alkaline phosphatase, total bilirubin, bicarbonate, BUN, calcium, chloride, creatinine, glucose, LDH, phosphorus, potassium, total protein, SGOT [AST], SGPT [ALT], sodium.
- e: Disease-specific tumor markers as appropriate (e.g. CEA, CA-19-9, CA125) should be drawn at specified times provided the patient has elevation of that specific tumor maker prior to study enrollment. Colorectal: CEA; Pancreatic: CEA and CA-19-9; Lung: CEA; Any other tumor types: PI with treating MD can advise which tumor markers are appropriate to follow.
- f: EKGs should be done pre-dose at all required time points.
- g: ECHO or MUGA to be performed at screening and again on C1D28 (acceptable window C1 D23-D29.) Thereafter, exam should be repeated every 12 weeks (+/-1 week.) The same modality used during screening should be used for all follow up exams.
- h: Tumor measurements and radiologic evaluation should occur every 8 weeks +/- 1 week. If a patient is on a dose hold, scans should be kept on original schedule and should not be shifted. Patients that have scans which reveal disease progression do not need to repeat end of treatment scans.
- i: Serum pregnancy test (women of childbearing potential) must be done within 7 days of C1D1.
- j: Pre-study tumor biopsy to occur between days -21 and day-1. When possible, it is preferred, but not required, that the pre-treatment biopsy be performed between days -7 and -1 of treatment in order to most accurately represent the baseline signaling activity prior to treatment. Platelet count and PT/PTT must be checked prior to procedure according to institutional guidelines and must be in acceptable range as defined in section 9.1.1.2.
- k: On treatment biopsy to occur ~2 weeks after trametinib dosing on day 15 (+/- 7 days.) Platelet count and PT/PTT must be checked prior to procedure on the same day, and must be in acceptable range as defined in section 9.1.1.2.
- 1: Complete PK schedule detailed in Section 9.3. Additional PK samples (single trough measurements only) required on day 1 of cycles 4, 8, and 12, not represented on this calendar.
- m: Includes pre-dose (0h), 2h, 4h, 6h, 8h draws on C1D7 and 23h draw (pre-dose) on C1D8. See section 9.3 for details.
- n: Includes pre- trametinib (1h), pre navitoclax (0h), and 2h, 4h, 6h, 8h post navitoclax draws on C1D14 and 23h draw (pre- trametinib) on C1D15. See section 9.3 for details.
- o: Single pre-dose (pre- trametinib and navitoclax) trough on C2D1. See Section 9.3 for details.
- p: At least 20 unstained slides are required. If a patient is having a tumor biopsy, less than 20 is acceptable with PI approval.
- q: Off study procedures should be performed within 14 days of last dose. Patients will be followed until the resolution or stabilization of all study-related toxicity and for a minimum of 30 days after removal from study or until death, whichever occurs first. Patients removed from study for unacceptable adverse event(s) will be followed until resolution or stabilization of the adverse event.

Part 1 (Phase 1b) Schedule C

	Pre- Study	C1D1	C1D7	C1D8	C1D14	C1D15	C1D22	C2D1	C2D15	C3D1, C4D1, etc	Off Study ^q
Trametinib		T	Т	Т	T			T		T	
Navitoclax		L	L	N	N	N	N	N	N	N	
Informed consent a	X										
Demographics	X										

					I	1					
Medical history	X										
Concurrent meds	X	X	XX								
Physical exam b	X	X		X		X	X	X	X	X	X
Vital signs ^c	X	X	X	X	X	X	X	X	X	X	X
Height	X										
Weight	X	X		X		X	X	X	X	X	X
Performance status	X	X		X		X	X	X	X	X	X
CBC w/diff, plts	X	X	X			X	X	X	X	X	X
Serum chemistry d	X	X	X			X	X	X	X	X	X
PT/PTT	X	X	X			X		X		X	X
Tumor Markers °	X							X		X	X
Urinalysis	X										
EKG ^f	X	X		X		X	X	X	X		
Echocardiogram or MUGA	X	Repeat	t on C1D2		5 days prior o e methodolog				every 12 we	eeks (use	
Ophthalmology exam	X		Re	epeated as	s needed only	if patient e	xperiences	vision ch	anges		
Adverse event evaluation		X								X	X
Radiologic evaluations/ Tumor measurements	X	Cycle 1	Day 1. Tu	umor mea	(by CT or MF surements are led for patien	e repeated of	every 8 wee	ks. Docu	ımentation	•	X
B-HCG	Xi										
Tumor biopsy	Xj					Xk					
PK blood draw ^l			Xm	Xm	Xn	Xn		Xº		X ¹	
Archival Tissue	Xp										
cfDNA blood draw		X						X		X	X

96

- T: Trametinib. Dose as assigned; **dose in the evening** on empty stomach, at least 1 hour before or two hours after food (there are no hematologic parameters that must be met to continue dosing with trametinib at the beginning of each cycle.)
- N: Navitoclax. Dose as assigned; dose in morning with food
- L: Lead-in dose of navitoclax. 150 mg daily in morning for 7 days, dosed as above.
- a: Informed consent can be signed within 28 days of C1D1.
- b: Complete physical exam required pre-study and on Day 1 of each cycle, including head, eye, ear, nose, throat (HEENT,) cardiovascular, dermatological, musculoskeletal, respiratory, gastrointestinal, and neurological systems. Limited or symptom directed physical exam at the discretion of the investigator is sufficient at all other visits.
- c: Vitals should include blood pressure, heart rate, respiratory rate, oxygen saturation, and temperature.
- d: Albumin, alkaline phosphatase, total bilirubin, bicarbonate, BUN, calcium, chloride, creatinine, glucose, LDH, phosphorus, potassium, total protein, SGOT [AST], SGPT [ALT], sodium.
- e: Disease-specific tumor markers as appropriate (e.g. CEA, CA-19-9, CA125) should be drawn at specified times provided the patient has elevation of that specific tumor maker prior to study enrollment. Colorectal: CEA; Pancreatic: CEA and CA-19-9; Lung: CEA; Any other tumor types: PI with treating MD can advise which tumor markers are appropriate to follow.
- f: EKGs should be done pre-dose at all required time points.
- g: ECHO or MUGA to be performed at screening and again on C1D28 (acceptable window C1 D23-D29.) Thereafter, exam should be repeated every 12 weeks (+/-1 week.) The same modality used during screening should be used for all follow up exams.
- h: Tumor measurements and radiologic evaluation should occur every 8 weeks +/- 1 week. If a patient is on a dose hold, scans should be kept on original schedule and should not be shifted. Patients that have scans which reveal disease progression do not need to repeat end of treatment scans.
- i: Serum pregnancy test (women of childbearing potential) must be done within 7 days of C1D1.
- j: Pre-study tumor biopsy to occur between days -21 and day-1. When possible, it is preferred, but not required, that the pre-treatment biopsy be performed between days -7 and -1 of treatment in order to most accurately represent the baseline signaling activity prior to treatment. Platelet count and PT/PTT must be checked prior to procedure according to institutional guidelines and must be in acceptable range as defined in section 9.1.1.2.
- k: On treatment biopsy to occur ~2 weeks after trametinib dosing on day 15 (+/- 7 days.) Platelet count and PT/PTT must be checked prior to procedure on the same day, and must be in acceptable range as defined in section 9.1.1.2.
- 1: Complete PK schedule detailed in Section 9.3. Additional PK samples (single trough measurements only) required on day 1 of cycles 4, 8, and 12, not represented on this calendar.
- m: Includes pre-dose (0h), 2h, 4h, 6h, 8h draws on C1D7 and 24h draw (pre-dose) on C1D8. See section 9.3 for details.
- n: Includes pre navitoclax (0h), and 2h, 4h, 6h, 8h post navitoclax draws on C1D14 and 24h draw on C1D15. See section 9.3 for details.
- o: Single pre-dose (pre-navitoclax) trough on C2D1. See Section 9.3 for details.
- p: At least 20 unstained slides are required. If a patient is having a tumor biopsy, less than 20 is acceptable with PI approval.
- q: Off study procedures should be performed within 14 days of last dose. Patients will be followed until the resolution or stabilization of all study-related toxicity and for a minimum of 30 days after removal from study or until death, whichever occurs first. Patients removed from study for unacceptable adverse event(s) will be followed until resolution or stabilization of the adverse event.

Part 2 (Phase 2) Schedule A (To be used if RP2D is to be given by Schedule A)

	Pre- Study	C1D1	C1D8	C1D15	C1D22	C2D1	C2D15	C3D1, C4D1, etc	Off Study ^p
Trametinib			Т	T	T	Т	Т	T	
Navitoclax		L	N	N	N	N	N	N	
Informed consent a	X								
Demographics	X								
Medical history	X								
Concurrent meds	X	X						X	
Physical exam ^b	X	X	X	X	X	X	X	X	X
Vital signs ^c	X	X	X	X	X	X	X	X	X
Height	X								
Weight	X	X	X	X	X	X	X	X	X
Performance status	X	X	X	X	X	X	X	X	X
CBC w/diff, plts	X	X	X	X	X	X	X	X	X
Serum chemistry d	X	X	X	X	X	X	X	X	X
PT/PTT	X	X	X		X			X	X
Tumor Markerse	X					X		X	X
Urinalysis	X								
EKG ^f	X	X	X	X	X	X	X		
Echocardiogram or MUGA	X	Repeat	on C1D2				1.) Every 12 Collow up). ^g	weeks (use same	
Ophthalmology exam	X		Repeated	as needed	only if pati	ent exper	iences visio	n changes	
Adverse event evaluation		X							X
Radiologic evaluation/Tumor measurements	X	followin	g Cycle 1	Day 1. Tu	nor measur	ements a	re repeated	ed every 8 weeks every 8 weeks. noved from study	X

98

Version Date: July 22, 2022

		for progres					
B-HCG	Xi						
Tumor biopsy	$X^{j,k}$			$X^{j,l}$			
PK blood draw ^m					Xn	X ^m	
Archival Tissue	X°						

- T: Trametinib. Dose as assigned; dose first in morning on empty stomach, at least 1 hour before food (there are no hematologic paramaters that must be met to continue dosing with trametinib at the beginning of each cycle.)
- N: Navitoclax. Dose as assigned; dose second in morning with food, at least 1 hour after trametinib
- L: Lead-in dose of navitoclax. 150 mg daily in morning for 7 days, dosed as above.
- a: Informed consent can be signed within 28 days of C1D1.
- b: Complete physical exam required pre-study and on Day 1 of each cycle, including head, eye, ear, nose, throat (HEENT,) cardiovascular, dermatological, musculoskeletal, respiratory, gastrointestinal, and neurological systems. Limited or symptom directed physical exam at the discretion of the investigator is sufficient at all other visits.
- c: Vitals should include blood pressure, heart rate, respiratory rate, oxygen saturation, and temperature.
- d: Albumin, alkaline phosphatase, total bilirubin, bicarbonate, BUN, calcium, chloride, creatinine, glucose, LDH, phosphorus, potassium, total protein, SGOT [AST], SGPT [ALT], sodium.
- e: Disease-specific tumor markers as appropriate (e.g. CEA, CA-19-9, CA125) should be drawn at specified times provided the patient has elevation of that specific tumor maker prior to study enrollment. Colorectal: CEA; Pancreatic: CEA and CA-19-9; Lung: CEA; Any other tumor types: PI with treating MD can advise which tumor markers are appropriate to follow.
- f: EKGs should be done pre-dose at all required time points.
